Colorectal cancer (CRC) is an important public health problem in the United States and Texas, particularly for the uninsured. CRC is the 2nd leading cause of cancer death in the United States and Texas^{1, 2}. Nationwide, 150,000 individuals are diagnosed, and 50,000 individuals die of the disease annually². Each year, CRC treatment results in over \$14 billion in costs nationally, and over \$3.7 billion in costs for Texas^{2, 3}. Uninsured patients are at particularly high risk for poor CRC outcomes. Uninsured patients are more likely to present with advanced stage CRC, and have worse stage-specific survival than other groups⁴. At John Peter Smith Health System (JPS), the main safety net health system providing care to uninsured patients in Fort Worth and Tarrant County, Texas, 63% of patients with CRC have advanced stage at presentation. *Overall, it is clear that CRC is an important public health problem, particularly for the uninsured*.

CRC screening with fecal occult blood tests, sigmoidoscopy, or colonoscopy can save lives. Randomized controlled trials have shown that screening with fecal occult blood tests (FOBT) or sigmoidoscopy reduces CRC incidence and mortality⁵⁻⁹. Observational studies have demonstrated similar results for colonoscopy¹⁰⁻¹². As a result, the US Preventive Services Task Force and the American Cancer Society have endorsed CRC screening for all individuals beginning at age 50 years^{13, 14}. The US Preventive Services Task Force does not endorse one test over others because modeling studies suggest that regular screening with fecal occult blood testing, sigmoidoscopy, or colonoscopy results in similar outcomes¹⁴⁻¹⁷. Because FOBT, sigmoidoscopy, and colonoscopy all appear to reduce CRC mortality, and because it is uncertain whether any one test is better than others, many support the idea that "the best CRC screening test is the one that gets done¹⁷."

CRC screening participation is suboptimal, particularly for uninsured patients age 50-64 years and minorities. National Health Interview Survey data show that screening participation, defined as being up-to-date with stool occult blood, sigmoidoscopy, or colonoscopy testing, was 55% for all individuals aged 50 to 75 years in 2008¹⁸. Marked variation in screening was noted by

Table 1. Baseline screening rates among uninsured JPS connection patients age 50 to 64 seen >1 time in a primary care clinic in 2011			
n Not Up-to-Date with Screening Screening, n Rate			

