Uninsured patients not up-to-date with CRC screening meeting the following criteria will be included:

- Age 50-64. This age group is at highest risk for screening non completion. Patients younger than age 50 will be excluded because screening is not routinely recommended for patients under 50. Patients older than 64 will be excluded because most of these patients would have screening access through Medicare insurance.
- Uninsured, but participants in JPS's medical assistance program for the uninsured. Uninsured patients have the lowest rates of screening participation, and therefore are most likely to benefit from screening outreach. Selecting patients who are uninsured, but enrolled in JPS's medical assistance program for the uninsured will ensure that any patient found to have a cancer or unresectable polyp will have access to surgical and/or medical oncology services. This is critical, because CPRIT funds do not allow for cancer care; offering screening without a system to care for patients with cancer would be unethical.
- One or more visits to a JPS primary care clinic within a year. This criterion establishes that patients have a baseline relationship with the JPS primary care system.
- Not up-to-date with colorectal cancer screening. We will apply National Committee on Quality Assurance Healthcare Effectiveness Data and Information Set (HEDIS) criteria to determine if patients are up-to-date with screening, defined by having had a colonoscopy within 10 years, a fecal occult blood test within one year, or a sigmoidoscopy within 5

Table 3: HEDIS codes used to measure CRC Screening			
Description	СРТ	HCPCS	ICD-9-CM Procedure
FOBT/FIT	82270, 82274	G0328, G0394	
Sigmoidoscopy	45330-45335,45337- 45342,45345	G0104	45.24
Colonoscopy	44388-44394,44397, 45355, 45378-45387, 45391, 45392	G0105, G0121	45.22, 45.23, 45.25, 45.42, 45.43

years⁴³. HEDIS criteria allow for using administrative claims data, including Current Procedural Terminology (CPT), International Classification of Diseases-9 (ICD9), and Health Care Common Procedure Coding System (HCPCS) codes to determine whether patients have had CRC screening tests. Logical Observation Identifiers Names and Codes (LOINC) will not be used because these are not routinely used within the JPS system.

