Sample size for Evaluation Aim C. The sample size for Evaluation Aim C is based on comparing the initial screening participation rate between the \$5 vs. the \$10 incentive groups. As is outlined in Section A.3, previous data suggest that financial incentives are effective for promoting complex healthy behaviors such as quitting smoking³⁹⁻⁴¹. Further, we believe that incremental (modest) incentives are likely to significantly increase screening completion. First, we assumed that a 10% or more difference in initial screening participation would be clinically meaningful. Second, we assumed that the screening completion rate associated with the \$5 group would be 43%, and that the rate for the \$10 group would be at least 53%. The 43% rate was chosen because our response to FIT invitations with our prior outreach program was 33%, and we would consider a 10% or more increase Version 8, June 29, 2015

in screening completion associated with the \$5 intervention over organized outreach alone to be clinically meaningful. Similarly, the 53% rate was chosen for the \$10 group because we would consider a 10% or more increase in screening completion associated with the \$10, rather than the \$5 group to be clinically meaningful. Under these assumptions, with an alpha=0.05, we estimated 1090 patients (n=545 in the \$5 group and n=545 in the \$10 group) would be required for 90% power to detect a statistically significant difference of 10% or more in initial screening participation. Because we recognize uncertainty in the estimating the expected difference between the two groups, and because we wanted to increase our ability to conduct exploratory comparisons of repeat FIT participation rates associated with the \$5 and \$10 groups, we increased the planned sample receiving financial incentives to 2,000 (n=1,000 in the \$5 group and n=1,000 in the \$10 group). Thus, we will have more than enough power to detect differences of 10% or more in initial screening participation.

Evaluation Aim D) Assess all CPRIT required outcomes, including increase in early stage cancer detection from baseline, as well as systems changes required to boost screening. To assess increase in early stage cancer detection from baseline, we will compute proportion of CRC patients with early stage cancer at baseline and at end of Year 3. JPS Cancer Registry data will be used for this computation. Rate of early stage cancer will be defined as:

Early Stage	# CRC patients with SEER Summary

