Cancer	Stage 0 or Stage 1
Detection Rate =	# CRC patients

program at JPS to other safety-net systems.

We will use a Chi-square test of proportions for comparing groups, and a p value <0.05 to signify statistical significance.

To assess systems changes required to boost screening, we will plan additional evaluations focused on the JPS health system. In addition to evaluating outcome change (as described above), it is also important to evaluate changes in processes related to transferring and expanding our outreach program at JPS. The purpose of this process evaluation is to gather information about the roll out process to enhance sustainability of the screening program, and enable translation of this program to other safety-net settings. To meet these objectives, we will monitor the screening program on a real-time basis. During weekly meetings between UTSW nurse (TBA) and JPS screening outreach team, the UTSW nurse will ask members of the outreach team about their experience with the program. She will maintain a detailed log of problems and successes. She will also document strategies and workarounds that JPS staff develop to tailor the program to their needs and resources. Similarly, barriers and facilitators of the outreach program at the health system level identified during JPS physician champion meetings with the principal investigator will be documented. Sustainability of the program will be enhanced because JPS staff will have access to systematically collected information about on the ground strategies that worked and did not work at the screening delivery level as well as at the health system level. In

addition, this information will also enable us to apply our knowledge of successfully establishing this

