Third, we will quantify the number of patients who have CRC and potentially precancerous polyps detected through screening outreach. CRC and polyp data will be collected by reviewing all colonoscopy and associated pathology reports for patients who undergo colonoscopies after having abnormal FIT tests. Additionally, we will query the JPS tumor registry to identify any program participants who had CRC diagnosed, and determine, through chart review, whether the CRCs were detected as a result of our screening outreach or through other mechanisms. With our plan to invite over 20,000 patients, taking into account our prior rates of FIT screening participation (33%), abnormal FIT results (12%), and detection rates of CRC (4.8%) and adenomas (46%) after abnormal FIT, we estimate that 38 patients with CRC and 364 patients with adenomas will be identified through our program.

REFERENCES

- 3. (2012). StatBite: National Costs for Cancer Care in 2010 in Billions of Dollars by Cancer Site. J Natl Cancer Inst 104, 13.

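### Aim D tests the early-stage share over registry colorectal cancers with no eligibility limit and no diagnosis window, so a stage shift in the population the program targets is diluted in proportion to that population's share of the registry

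*Combined protocol and SAP*

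**What the plan says.** Evaluation Aim D, in the Biostatistics section, starts its first component with "To assess increase in early stage cancer detection from baseline". The plan will "compute proportion of CRC patients with early stage cancer at baseline and at end of Year 3", and "JPS Cancer Registry data will be used for this computation". The rate has as its numerator the "CRC patients with SEER Summary" Stage 0 or 1, and as its denominator the number of colorectal cancer (CRC) patients. The formula carries no further condition. The test is stated as: "We will use a Chi-square test of proportions for comparing groups, and a p value <0.05 to signify statistical significance". Aim D gives no expected case count, effect size or power, and does not say over what period diagnoses are counted at either time point.

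The program reaches a narrower group. Criteria for Inclusion of Subjects requires age 50-64, uninsured status with membership of the JPS assistance program, a JPS primary-care visit within a year, and not being up to date with screening. On the upper age limit it says: "Patients older than 64 will be excluded because most of these patients would have screening access through Medicare insurance".

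Evaluation Aim A lists six eligibility conditions for its denominator and applies them at both baseline and end of Year 3. Aim D has no such list.

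**The concern.** Aim D is one of the listed primary evaluation aims, and its early-stage rate has a formal significance test. The question behind the test is whether outreach moves diagnosis to an earlier stage. Outreach can do that only in people it reaches. A registry cancer in someone too old, too young, insured, or without a primary-care visit enters both periods with a stage mix that the program cannot influence. Such cases pull the registry-wide change towards zero, and a non-significant result becomes hard to read.

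The missing diagnosis window adds a second uncertainty. If the follow-up rate is taken over Year 3 diagnoses only, program cancers found in Years 1 and 2 are left out. If it is taken over all diagnoses through Year 3, they are counted. The text allows both readings, and the choice could be made after the data are seen.

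**Working it through.** **The plan's own figure.** Aim D has no sample-size figure to reproduce. The nearest is the expected program yield under Secondary analyses (third): 20,000 × 0.33 × 0.12 × 0.048 = 38.0 cancers, which matches the stated 38. This counts program-detected cancers, not all cancers in eligible patients, so it is not directly comparable with the case numbers below.

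**Inputs.**
- Baseline early-stage share: 37%, from 100% − 63%. The Background says "63% of patients with CRC have advanced stage at presentation". Treating everything not advanced as Stage 0 or 1 is an assumption, because advanced is not defined.
- Eligible share of registry cancers, *f*: not in the documents. Range assumed: 25% to 60%.
- Gain among eligible patients: 20 points, 37% to 57%. Assumed for illustration.
- Same baseline stage mix inside and outside the eligible population, and no change outside it. Assumed.
- Two-sided 0.05 and 80% power. Aim D does not state sidedness; Aims A to C are two-sided.

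**Dilution.** Registry-wide change = *f* × change among eligible patients = *f* × 20 points.

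**Cases per period.** With p̄ the mean of p₁ and p₂,

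n = [1.96 √(2p̄(1−p̄)) + 0.842 √(p₁(1−p₁) + p₂(1−p₂))]² / (p₂−p₁)².

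For 37% against 57%, n = 96.6, so 97 eligible cases. The registry cases needed to supply them are 96.6 / *f*.

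| *f* | Registry-wide change | Registry cases per period, unrestricted test | Registry cases per period, restricted test | Ratio |
|---|---|---|---|---|
| 25% | 5 points (37 to 42%) | 1,499 | 386 | 3.9 |
| 50% | 10 points (37 to 47%) | 381 | 193 | 2.0 |
| 60% | 12 points (37 to 49%) | 266 | 161 | 1.7 |

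Restriction discards cases but needs fewer registry cases overall. The advantage narrows as *f* rises and is still present at *f* = 90% (119 against 107).

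**A second model.** This one fixes the 38 program cancers and lets the gain follow from them. Assumed: 60 to 200 registry cancers a year, *f* from 30% to 70%, 60% to 80% early stage among program-detected cancers, 37% among all others, and three-year windows in both periods. The unrestricted rate moves from 37% to between 38.5% and 46.1%, with power 7% to 42%. The restricted rate moves to between 39.1% and 67.3%, with power 9% to 89%. Restricted power was higher in every scenario.

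**Timing.** Sub-Study Procedures, written after nearly two years, assumes at least 329 abnormal FITs and a 36% return rate. With 10% to 14% abnormal (assumed, around the plan's 12%), 329 / (0.36 × 0.14) = 6,528 and 329 / (0.36 × 0.10) = 9,139. So roughly 6,500 to 9,100 people had been invited by then, under half of 20,000. Because 329 is a stated minimum, this is only a rough guide.

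**The case against.** **The unrestricted denominator is an inference.** Aim D never says that it uses all registry cancers, and no passage describes the registry's case mix. Sources of Research Material gives the registry's purpose as finding enrolled patients who develop CRC during follow-up, and the third secondary analysis will "query the JPS tumor registry to identify any program participants who had CRC diagnosed". This stands in part: it is why the point is worded as dilution to the extent that the registry holds other cancers. Neither passage repairs Aim D, however. Enrolled patients followed forward cannot form a baseline group, and the secondary analysis is a count with attribution, not a stage comparison.

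**A system-wide figure has a purpose.** Early-stage detection is a funder-required outcome, and the 63% is itself quoted for JPS CRC patients generally. That is a good reason to keep the registry-wide rate as a description. It does not make that rate the better one to test.

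**The sizes are assumed.** The share, the 20-point gain and the common baseline stage mix have no source in the documents. That stands. So does the point that restriction may not be enough: power is only 9% at the low end of the second model.

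**Stronger readings that the documents do not support.**
- A reader might infer that the measure is mistimed, falling after a first-round peak. The text defines no window, invitations are spread over time, newly eligible patients enter in Years 2 and 3, and 2,124 people get a first invitation late in Year 2. Much first-round detection could fall in Year 3.
- A reader might infer that counting Stage 0 is an error. Aim D sets out to measure early-stage detection, and Stage 0 is early stage under its own definition. A fall in advanced cancers would be a different outcome.
- A reader might infer that a null result would carry no information. At a 60% share, a 12-point shift is detectable with 266 cases per period.

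**Conclusion.** The concern holds as a cheap improvement. As written, Aim D tests a rate with no eligibility limit, while the program targets a defined subset and Aim A shows that the matching restriction can be written down. Any stage shift among eligible patients is multiplied by their share of registry cancers. With an assumed share of 25-60% and an assumed gain from 37% to 57%, the tested change is 5-12 points, and the unrestricted test needs about 3.9 to 1.7 times as many registry cases as the restricted one. These sizes depend on the assumed share, the assumed gain, an equal baseline stage mix in both groups, and reading early as not advanced. The direction of the dilution does not depend on the particular share or gain.

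The diagnosis window is undefined, which is a separate gap. Only under the Year 3 reading would program cancers from Years 1 and 2 be lost. The randomized comparisons in Aims B and C are unaffected.

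**What to change.** In Evaluation Aim D:

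1. Make the tested comparison the early-stage proportion among registry CRCs in patients who met the Aim A eligibility criteria at a data pull before diagnosis. Apply the rule identically in both periods.
2. Keep in patients who later leave JPS Connection or have no recent primary-care visit. Criteria for Exclusion of Subjects deliberately retains them, so a filter requiring coverage or a visit at the time of diagnosis would drop people the program invited.
3. Count all diagnoses from first invitation to end of Year 3, against a pre-program period of equal length.
4. Report the number of cases in each period and a confidence interval for the difference.
5. Keep the registry-wide proportion as the funder's descriptive outcome.

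The cost is SAP wording and a link between sources the plan already uses: the registry and the administrative records. The plan already intends annual screening rates for years before the program, so earlier data pulls look feasible. The tested comparison will have fewer cases. Some dilution will remain, because the Aim A criteria include patients already up to date (39% at baseline), who were not invited.

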All patients	16,905	10319	39%
Race/ethnicity			
White	6,187	4081	34%
Black	3,968	2386	40%
Hispanic	4,774	2745	43%
Other	1,976	1107	44%

race/ethnicity. Screening rates were 51% for Blacks and 39% for Hispanics, compared to 57% for

Whites. Most strikingly, uninsured 50 to 64 year olds had the lowest rate of screening participation, at just 20%, markedly lower than the 55% screening rate noted for insured patients age 50 to 64. Data from JPS has also shown low screening rates of among uninsured 50 to 64 year olds¹⁹. Currently, just 39% of uninsured 50 to 64 year olds seen regularly in a primary care clinic are up-to-date with screening (Table 1).

Our prior CPRIT-sponsored Evidence Based Prevention Program demonstrated that screening rates for the uninsured and minorities can be dramatically improved through screening outreach. The goals of our prior program were to deliver CRC screening invitations to 2,080 patients, determine if an organized outreach invitation strategy to complete screening boosted screening compared to usual care, and determine if screening completion was higher when stool occult blood testing with fecal immunochemical test (FIT) versus colonoscopy screening were offered. The program was set at JPS, a safety-net health system that serves a large, very diverse group of uninsured patients. We identified 5,994 uninsured patients, age 54 to 64 years, not up-to-date with CRC screening, and randomly assigned them to one of three screening strategies: usual care (n=3914 patients), organized invitation to FIT screening (n=1600 patients), and organized invitation to colonoscopy screening (n=480 patients). Organized outreach consisted of a mailed invitation to complete screening, information regarding the importance of screening, and, for the FIT group, a FIT kit. Patients assigned to the FIT and colonoscopy screening strategies also received processes to promote screening completion consisting of 2 automated and up to 2 "live" telephone reminders to complete screening, navigation to colonoscopy for screening or diagnostic purposes, and results reporting. Program processes were developed in close collaboration with clinical service providers at JPS such as the GI lab. The tracking database used to prompt and track outreach activities was developed and pretested at UT Southwestern.

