We must expand this organized outreach program to all uninsured individuals age 50 to 64 not up-to-date with screening at our safety-net health system. We have extracted health system encounter data for all patients age 50 to 64 seen \geq 1 times in a primary care setting in 2011 who participate in JPS' medical assistance program for the uninsured. Out of 16,905 patients meeting these criteria, 6,586—39%—are up-to-date with screening, defined by having an FOBT in the last year, sigmoidoscopy within 5 years, or colonoscopy within 10 years (Table 1). Thus, as of 2011, 10,319 patients need screening. Screening rates are suboptimal among all major racial/ethnic groups (Table 1). Our prior CPRIT program delivered screening invitations to 2,080 patients, a much smaller group, and limited invitations to patients age 54 to 64. Now that our outreach program has been developed and shown to substantially boost screening, we need to expand outreach to all eligible individuals.

To enable sustainability of program activities, primary responsibility for screening outreach delivery must be transferred from UT Southwestern to JPS staff, and JPS must be equipped to run the outreach program. Previously, all screening outreach was delivered by UT Southwestern personnel. Specifically, a UT Southwestern Moncrief Cancer Institute nurse manager, and a UT Southwestern medical assistant created and mailed all invitations, made all reminder phone calls, delivered all testing results, arranged all follow up colonoscopy tests for patients requiring colonoscopy, and managed our screening tracking database. All UT Southwestern personnel were supervised on a day to day basis by a gastroenterologist and clinical researcher at UT Southwestern. Because the colonoscopy tests and all pre and post colonoscopy visits were conducted at JPS, this work required close interfaces with the JPS clinics and gastrointestinal endoscopy laboratory, as well as intermittent consultation with two JPS primary care physicians who were key physician champions of our program. This meant that UT Southwestern in effect served as an intermediary between JPS patients and JPS staff, and also worked through JPS physician champions to mediate any challenges

Version 8, June 29, 2015

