Additional patients will be assessed for inclusion/exclusion criteria annually in Years 2 and 3 of the program. Each year, patients who newly meet our inclusion/exclusion criteria will be included in the program. For example, patients newly turning 50 in year 2 or 3 meeting all other inclusion/exclusion criteria will receive screening outreach. Similarly, a 60 year old patient new to the JPS system and meeting inclusion/exclusion criteria will also receive screening outreach. We think this approach reflects the ideal implementation of a standing CRC outreach program.

Sources of Research Material:

There are several sources of research material for this project:

- Administrative and electronic medical record databases at JPS. These data systems will be used to identify patients meeting inclusion/exclusion criteria, and to record outcomes of screening invitation.
- **Results of fecal immunochemical tests (FIT).** Patients will be invited to complete screening with a one-sample FIT. These kits will be processed by the JPS clinical lab, and the results will be recorded in the electronic medical record. Results of testing, including whether the test was abnormal or normal, and the level of hemoglobin present in the sample, will be collected
- **JPS cancer registry**. This resource will be accessed to identify patients enrolled in the screening program who develop CRC during the follow up time frame.
- **Study tracking database**. This database will record in real-time delivery of all screening interventions, and outcomes of the interventions. In addition, process variables, such as time spent on phone with patients, failed mailings due to wrong address will be collected. The study tracking database has been created for exclusive use by screening program personnel.
- Interviews of JPS personnel who will be conducting outreach interventions. The purpose of these interviews will be to understand the challenges to implementation of the outreach program within the health system.

Variable	Justification	Source
Baseline characteristics and elig	gibility criteria	
first name, last name	Required for delivery of	JPS administrative and
	screening invitations	electronic medical record
date of birth	Required for eligibility criteria	databases
Sex	Screening rates can differ by	
	sex	
Race/ethnicity	Screening rates may differ by	
	race/ethnicity	
Primary language	Use to identify preferred	
	language for study interventions	
Home address	Required for screening	

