Secondary analyses. We plan to conduct several secondary analyses. First, we recognize that results from Evaluation Aim A, in which baseline screening rates will be compared to follow up screening rates at year 3, could be confounded by time trends in CRC screening rates, which generally have been increasing over time. Accordingly, we will compare the observed rate of CRC screening in Year 3 to the expected rate of CRC screening based on time trends in screening at JPS. The expected rate will be estimated using the secular trend for CRC screening using annual screening rates for each of the 7 years 2006-2011 prior to start of our prevention program in 2012. All rates will be standardized by gender and age strata (50-54, 55-59, and 60-64 years) to the population distribution of men/women and these age strata for 2012, and a standardized incidence ratio (SIR) will be computed. An SIR greater than 1, with an associated 95% confidence interval that does not cross 1 will be interpreted as evidence to support impact of our outreach intervention beyond time trends in CRC screening rates. We have previously used this approach to assess impact of a University of Texas health plan policy that waived copays for colonoscopy screening on CRC screening rates which began in 2009, in which we compared colonoscopy uptake 2002-2008 to uptake after policy institution⁴⁶.

Version 8, June 29, 2015

Second, to identify factors independently associated with screening outcomes, we will construct several logistic regression models. For example, to identify predictors of initial screening completion, we will create a model using initial screening completion rate as the primary outcome (dependent) variable, and several potential predictors of completion. Predictors considered for model inclusion will include age, sex, race/ethnicity, frequency of primary care visits, exposure to the screening outreach program, and exposure to financial incentives. A similar model will be created with the outcome of programmatic screening as the dependent variable. For these exploratory analyses, 2-sided p values of 0.05 will be considered statistically significant.

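### The Aim A trend analysis standardises for sex and age only, and the primary comparison for nothing, although baseline screening ran from 34% to 44% by race/ethnicity; a race-standardised version should be reported

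*Combined protocol and SAP*

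**What the plan says.** Evaluation Aim A compares the proportion up to date at baseline and at the end of Year 3 by an unadjusted two-sided chi-square test at 0.05. The denominator is everyone meeting six eligibility criteria at each time point. The population is open: under Criteria for Exclusion of Subjects, newly eligible patients are added in Years 2 and 3.

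The first of the Secondary analyses recognises that time trends could confound this comparison and adds a standardised incidence ratio (SIR). "The expected rate will be estimated using the secular trend for CRC screening using annual screening rates" from before the program. On adjustment it says "All rates will be standardized by gender and age strata (50-54, 55-59, and 60-64 years"), with 2012 as the standard population. The decision rule is: "An SIR greater than 1, with an associated 95% confidence interval that does not cross 1 will be interpreted as evidence" of an impact beyond trend. No minimum effect is set.

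On race/ethnicity, the Background states "Screening rates are suboptimal among all major racial/ethnic groups (Table 1"). The Table 1 rows (patients, number not up to date, rate in %) include "White 6,187 4081 34" and "Black 3,968 2386 40". The variable table under Sources of Research Material justifies collecting the variable thus: "Screening rates may differ by" race/ethnicity. In the analysis plan it appears only as a candidate predictor in exploratory logistic models, which adjust neither the chi-square nor the SIR.

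**The concern.** Aim A compares two cross-sections of a changing population several years apart. A standardised comparison protects only against changes in the variables it standardises for. Race/ethnicity is the one patient characteristic for which the documents give screening rates in this health system; they give none by sex or age band. It is collected for much the same stated reason as sex, yet only sex is used.

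If the racial/ethnic mix differs between the compared years, part of the difference in rates reflects who was counted. It could be credited to outreach, or it could hide a real gain. The samples are so large, and the SIR rule so free of any minimum effect, that even a small difference of this kind can reach significance.

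**Working it through.** **Inputs.** Table 1 counts: White 6,187 patients (4,081 not up to date), Black 3,968 (2,386), Hispanic 4,774 (2,745), Other 1,976 (1,107). Sample size under Aim A: at least 20,000 per time point; Table 1 itself has 16,905. Predicted change: 39% to 49%.

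**1. Reproduce the plan's figures.** Rate = 1 − (not up to date / n).

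| Group | Share | Rate |
|---|---|---|
| White | 36.6% | 34.0% |
| Black | 23.5% | 39.9% |
| Hispanic | 28.2% | 42.5% |
| Other | 11.7% | 44.0% |

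The groups sum to 16,905 and 10,319, and the overall rate is 6,586/16,905 = 38.96%. This agrees with the text: "Out of 16,905 patients meeting these criteria, 6,586—39%—are up-to-date with screening". The Aim A power claims also hold: power exceeds 99.9% for rises of 10 and of 5 points.

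**2. Effect of mix alone.** Hold the group rates fixed (no program effect) and move a share s from White to another group: change = s × (rate of receiving group − 0.3404).

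- To Hispanic: 0.10 × (0.4250 − 0.3404) = 0.85 points; with s = 0.05, 0.42 points.
- To the other three groups in proportion (combined rate 41.8%): 0.10 × (0.4180 − 0.3404) = 0.78 points.

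**3. Aim A chi-square.** At n = 20,000 the standard error of the difference is √(2 × 0.39 × 0.61 / 20,000) ≈ 0.0049, so the critical difference is 1.96 × 0.0049 ≈ 0.96 points (1.04 at n = 16,905). Chance of a significant rise = 1 − Φ(1.96 − z), with z the expected difference over its standard error.

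| White-to-Hispanic shift | z | Chance |
|---|---|---|
| none | 0 | 2.5% |
| 5 points | 0.87 | about 14% |
| 10 points | 1.73 | about 41% |

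A shift of 11 to 12 points puts the expected difference at the critical value, where the chance is about one half.

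**4. SIR.** SIR = observed rate / expected rate, here with 38.96% as a fixed expected rate. The plan names no interval method, so two were tried: Poisson, lower limit = SIR × exp(−1.96/√observed count), and binomial on the observed rate. Off-trend shift needed for the point estimate alone to meet the rule:

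| Receiving group | n = 20,000 | n = 16,905 |
|---|---|---|
| Other | 6.9–8.8 points | 7.5–9.5 |
| Hispanic | 8.1–10.3 | 8.8–11.2 |
| All three, in proportion | 8.8–11.2 | 9.6–12.2 |

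(Binomial to Poisson.) That is about 7 to 12 points; if all of it went to Black patients, 12 to 16. For a proportional shift at n = 20,000, the chance of meeting the rule with no program effect is 0.6–2.5% with no shift, 8–20% at 5 points and 40–61% at 10 points (Poisson to binomial). Allowing for error in the extrapolated expected rate would widen the interval and raise the shift needed.

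**5. Upper bound.** Replacing every White patient in proportion: 0.366 × 0.0776 = 2.84 points, SIR 1.073. Giving everyone the highest group rate: 43.98 − 38.96 = 5.0 points, SIR 1.129. The predicted effect is 10 points, SIR 0.49/0.39 = 1.256.

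**6. With race/ethnicity in the strata**, the SIR in each of these mix-only cases returns to 1.000, since group rates are held fixed.

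**The case against.** The strongest reply is that the harm depends on a shift nobody has shown. Nothing in the documents gives the mix by year or says that it was changing, and both Aim A cross-sections apply the same eligibility criteria in one health system. An 11 to 12 point move out of a White share of 36.6% means replacing about a third of those patients. This stands: the shift is an assumption throughout.

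Second, the SIR compares Year 3 with a projected trend, so steady drift in mix is largely in the expected rate already. This also stands, and only off-trend change biases the SIR. The chi-square has no such protection.

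Third, Table 1 is crude. Part of the 34% to 44% spread may reflect age or sex, which the SIR already handles. The documents do not allow that part to be separated.

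Fourth, age-sex standardisation is a reasonable choice for a secondary analysis, and race/ethnicity does enter the logistic models. Those models are exploratory, however, and leave the Aim A comparison and the SIR unadjusted.

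A reader might infer that a change in mix could pass for the whole predicted effect, or that an 11 to 12 point shift would by itself be declared significant. Neither is supported: the ceiling is about half the prediction, and at that shift significance is roughly an even chance.

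**Conclusion.** The omission is real but modest. Neither the SIR nor the primary Aim A comparison accounts for a collected variable that the plan's own data link to screening. If the mix shifted by 5 to 10 points from White to Hispanic patients, the chance of a spurious significant rise in the chi-square would go from 2.5% to between about 14% and 41%. An off-trend shift of roughly 7 to 12 points would carry the SIR point estimate past its rule.

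These figures assume fixed group rates at the Table 1 values, no contribution of age or sex to the spread, 20,000 patients per time point for the probabilities, and, for the SIR, an expected rate known without error. The direction is not predictable: a shift towards White patients would mask a gain. A rise near the predicted 10 points could not be explained by racial/ethnic mix alone; a rise of one or two points could. The documents do not support concluding that the mix did change or that any program effect would be an artefact.

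**What to change.** 1. Report the racial/ethnic mix at baseline, at the end of Year 3 and for each trend year. If it is stable, the question is closed.
2. Beside the crude Aim A rates, show baseline and Year 3 rates standardised by sex, age band and the four Table 1 groups to one common distribution.
3. Add race/ethnicity to the SIR standardisation, or prespecify this as a sensitivity SIR where coding for 2006–2011 is complete enough.
4. Interpret the SIR by its size as well as by whether its interval excludes 1.

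The cost is a few sentences in the analysis plan and one more stratification variable; Data Sources and Data Tracking already lists race/ethnicity for extraction at baseline. There are downsides. Cells rise from 6 to 24 (2 sexes × 3 age bands × 4 groups). In Table 1 the Other group averages 1,976 / 6 ≈ 329 per cell, and actual cells will be uneven. Intervals will be slightly wider. The race-standardised SIR also depends on coding in the earlier trend years, which the documents do not describe; this is why a sensitivity analysis is an acceptable alternative.
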